6.6 OVERDOSE

Women will be advised to take one tablet only per day.

In the participant's diary, there will explicit information including contact details in the case of overdose. Should any participant take more than the prescribed dose, she will be asked to contact the obstetric triage area. She will be assessed by a member of the clinical care team

CR007-T01 v4.0 PIPIN Protocol Version 5.0 17/05/2019 Page **23** of **45**

with a member of the trial team informed as soon as possible. Bloods will be obtained for LFTs, renal function and CK, and the participant will be monitored for as long as is clinically necessary as judged by her attending obstetrician. There is no specific treatment in the event of overdose, and participants should be treated symptomatically and supportive measures instituted as required.

Following overdose, continuation of the trial drug will be a discussed between the participant, her obstetric team and the research team. Details of discontinuation of treatment will be reported in the medical notes.

6.7 OTHER MEDICATIONS

6.7.1 Non-Investigational Medicinal Products

There are no NIMPs used in this CTIMP

6.7.2 Permitted Medications

All medications other than those detailed in the SPC and 6.7.3 prohibited medications are permitted.

Medications that participants have been prescribed pre-pregnancy and which have been continued during the pregnancy as per the supervising clinician responsible for participant care may be taken during the trial.

6.7.3 Prohibited Medications

Should any of the below prohibited medications be inadvertently co-administered with the IMP, the participant should contact their obstetric team and attend for assessment as required.

Erythromycin and clarithromycin

Macrolide antibiotics have been shown to cause a small but significant increase in the Cmax and actual body exposure of patients to pravastatin when the two are co-administered. As erythromycin is only administered to patients with ruptured membranes (who are excluded from this trial) this is unlikely to occur. Clarithromycin will occasionally be given to patients when there is a suspicion of atypical bacteria lower respiratory tract infection

Fibrates

There is an increased rate of muscle related adverse events with concomitant use and therefore fibrates will be prohibited.

Colestyramine

40 to 50% reduction in bioavailability of pravastatin if administered concomitantly; no change if pravastatin administered one hour before OR four hours following cholestryramine. Not prohibited, but to be dosed as above.

Ciclosporin

Prohibited due to a 4 fold increase in the systemic exposure of pravastatin. As ciclosporin use is associated with preterm birth and low birth weight infants, these patients will be excluded from the trial.

7. STUDY ASSESSMENTS

7.1 SAFETY ASSESSMENTS

Safety assessments

We will collect data on side effects from all participants using a self-reported daily questionnaire to report any potential adverse events. Baseline and day 7 LFTs and CK will be used to monitor for hepatotoxicity or muscular toxicity.

7.2 STUDY ASSESSMENTS

Details of all sampling, processing and reporting of all blood tests can be found in the 'Working Practice Document'.

A. Screening

Demographics including gestational age and EDD, blood pressure, CTG and fetal fibronectin and/or cervical dilation will be collected as per local protocol for patients presenting with threatened preterm labour.

Following verbal consent, but prior to formal written consent, a cervical length scan may be required to assess eligibility and thus may be considered a screening condition.

B. Randomisation

Following written consent and randomisation, bloods for haemoglobin, renal function, LFTs, CK and an inflammatory profile with pravastatin levels will be taken.

C. Daily Until Discharge / Delivery / Completion of Treatment phase (whichever occurs soonest)

For participants admitted for monitoring or treatment, an inflammatory profile will be obtained twice on day 1 (baseline and at or around 12 hours post dose), daily thereafter whilst an inpatient, and at day 7. Serum pravastatin levels will also be collected at this time.

D. Throughout Duration of Treatment Phase

Contraction frequency will be self-monitored and recorded in the participants study diary. This may either through inpatient CTG monitoring or participant self-monitoring.

AEs may be recorded at any point, either by recording in the participant diary, verbal report to the trial team or through assessment of participant electronic health records.

E. At the Day 7 Trial Visit

This will occur at a mutually agreed location, either in the trial hospital or the participant's home. Compliance will be assessed via the trial diary and the bottles of treatment, the trial diary collected with its included information about AEs and contraction frequency, and bloods for an inflammatory profile, serum pravastatin levels, and LFTs / CK taken.

F. At Delivery

Bloods will be obtained for an inflammatory profile from maternal serum and umbilical cord. If delivery occurs within the treatment phase (7 days), as well as serum and cord samples also will be obtained for pravastatin levels. Apgars at 1,5 and 10 minutes be recorded if obtained.

G. At or around EDD + 28 days

Information for maternal and neonatal outcomes (see section 2.2.2 for details) will be assessed. This will not require a direct participant visit as this information will be obtained from the participant and baby's electronic health records.

Participants will be contacted by their preferred method of contact and acceptability of the trial discussed with them.

CR007-T01 v4.0 PIPIN Protocol Version 5.0 17/05/2019 Page **25** of **45**

The table below summarises this information.

Assessment or outcome	Screening	Randomisation	Day 1	Daily until discharge	Day 7	At Delivery	28 days post EDD
Clinical Measures				J			
Blood pressure	Х						
Fetal Fibronectin / Cervical Length	Х						
/ cervical dilation (one only required)	x						
Contraction Frequency	Х		Х	Х	Х		
Biochemical Measures							
Urea		Х	Х				
Serum creatinine		Х	Х				
Albumin		Х	Х		Х		
Liver transaminases		Х	Х		Х		Х
Inflammatory Profile		Х	Х	Х	Х	Х	
Haematological Measures							
Haemoglobin		Х					
Maternal							
Maternal mortality/ morbidity		Х	Х	Х	Х	Х	Х
Serious adverse events or reactions		Х	х	x	х	x	x
Routine CTG		Х	Х	Х	Х		
Serum Pravastatin			Х	Х	Х	Х	
Fetal & Neonatal Measures							
Gestational age (from EDD by ≤ 16 week scan)	х					x	
Cord inflammatory profile						Х	
Cord pravastatin levels						Х	
Apgar score at 1,5,10 minutes						Х	
Congenital anomalies	Х					Х	
Neonatal mortality/ morbidity						Х	Х
Length of maternal and perinatal hospital stay and location						х	X

7.3 COMPLIANCE ASSESSMENTS

Treatment Compliance will be recorded as described in paragraph 6.5.

7.4 LONG TERM FOLLOW UP ASSESSMENTS

All participants will be consented for long term (5 years) access to both maternal and baby notes. Following completion of the treatment phase (7 days / until delivery), participants will continue to be monitored for potential adverse effects via the electronic health record up until EDD +28 days. Participants will also be consented for preferred method of contact follow up for a period of up to 2 years. Should additional funding be secured, a 2 year follow up of maternal and child health in the form of medical notes review, questionnaire completion or developmental testing may be considered for which separate ethical approval will be sought.

There are no follow up visits planned after EDD + 28 days at this time.

7.5 STORAGE AND ANALYSIS OF SAMPLES

Fetal fibronectin samples will be obtained, analysed and disposed of within the assessing clinical area as per protocol.

Blood tests:

- 1) For baseline renal function as well as baseline and day 7 liver function and CK, these samples will be obtained in line with local protocol and processed via the NHS site central laboratory. They will then be disposed of after as per routine laboratory protocol.
- 2) All additional blood tests obtained for the purpose of this study will be obtained from the participant in line with local guidelines and transported to QMRI for processing, storage and analysis. For details of blood sampling techniques, sample processing and analysis, please see the Working Practice Documents.
 - a. Pharmacokinetic / pravastatin monitoring samples will be analysed in the Mass Spec Core (QMRI) in such a way as to maintain study blinding. For samples for spectroscopy analysis, samples will be re-aliquoted, and study ID will be replaced by an anaylsis ID by an independent person. The Mass Spec Core will maintain the link between study ID and analysis ID and ensure this is not revealed to the study team Samples will be analysed as per their 'analysis ID' in batches of 6 or more at a time to further ensure blinding remains secure. Results will be recorded on an analysis ID-specific CRF, and the analysis ID and study ID only linked back together at the time of unblinding of the study.
 - b. 'Inflammatory Profile' analysis will occur in the Tommy's Lab (W1.20, QMRI) by a trained individual following study specific procedure. For more detail of this, please see Working Practice Documents.
- 3) Consent will be sought for the long term storage of both maternal serum and cord blood, which will be done so in the Edinburgh Reproductive Tissue BioBank (ERTBB) in line with their protocols. The ERTBB is located in the QMRI, [name].

8. DATA COLLECTION

Data will be collected by the trial team from the participant verbally and confirmed where possible in the medical records (demographics (age, educational attainment, ethnicity, and Community Health Index (CHI) number for participant and their baby when born), details of

CR007-T01 v4.0 PIPIN Protocol Version 5.0 17/05/2019 Page **27** of **45**

previous pregnancies, blood test results, time to delivery), by direct monitoring (contraction frequency) and Participant questioning (side effect reporting via questionnaires, compliance, acceptability, side effects). Results of blood tests processed outwith NHS laboratories will be collected directly from the analysing team by the research team. Contact details will include address, preferred method of contact and GP details.

Both pCRFs and eCRFs will be used, with all data to be held in a secure database as detailed below. For participants being discharged home who remain on the study drug, their trial diary will contain areas for recording contraction frequency, medication compliance and side effect reporting. These will be collected by the research team at the day 7 trial visit.

At or near 28 days post EDD, participants will be contacted using their preferred method of contact, thanked for their involvement and asked for feedback, in the form of a short questionnaire. End of trial participation will be recorded in the CRF and medical notes, if available locally.

8.1 SOURCE DATA DOCUMENTATION

Source data is defined as all information in original records and certified copies of original records or clinical findings, observations, or other activities in a clinical trial necessary for the reconstruction and evaluation of the trial. Source data are contained in source documents.

Source documents are original documents, data and records where source data are recorded for the first time.

Data will be sourced from the participant's own and their babies Medical records, which may be paper or electronic. Data will also be sourced from medication charts, and either electronic or paper laboratory results. The study diary is source data and will be transcribed on to pCRF, or following development and Sponsor approval, an identical eCRF.

8.2 CASE REPORT FORMS

All case report forms (paper and electronic) for this study will be approved the ACCORD Monitor prior to use (as per the sponsors SOP ACCORD SOP CR013 CRF Design and Implementation).

This trial will begin using a pCRF, with a direct replica eCRF used later following Sponsor Approval.

8.3 TRIAL DATABASE

Trial database will be developed and managed by the Edinburgh Clinical Trials Unit. Data will be entered by the Chief Investigator, Clinical Research Fellow and Clinical trials manager, as well as by suitably trained and delegated individuals. This data will be anonymized and will be kept for 5 years in a secure fashion.

9. DATA MANAGEMENT

9.1.1 Personal Data

The following personal data will be collected as part of the research:

Participant's CHI Number, age, initials, ethinicity, estimated date of delivery, height and weight at booking.

Personal data will be stored by the research team in a secure, locked cabinet in a code-access controlled room in Royal Infirmary of Edinburgh (NHS Lothian). Only the

CR007-T01 v4.0 PIPIN Protocol Version 5.0 17/05/2019 Page **28** of **45**

research team will have access to personal data. The code break can be provided by a member of the research team, as can location of the key for the cabinet. Personal data will be stored for 25 years in line with MRC guidelines on clinical trials involving pregnant participants.

9.1.2 Transfer of Data

All data collected or generated by the study (including personal data) will not be transferred to any external individuals or organisations outside of the Sponsoring organisation(s).

9.1.3 Data Custodian

The data custodian is [name]

9.1.4 Data Controller

The data controller is ACCORD

10. STATISTICS AND DATA ANALYSIS

10.1 SAMPLE SIZE CALCULATION

A formal power calculation is not considered necessary or appropriate for a feasibility study: the primary outcome in this feasibility study is recruitment rate. Together with data on time to delivery, contraction frequency and participant acceptability, this will be used to determine whether a large randomised trial is warranted and feasible. The remaining outcomes will be used either as safety markers, or to inform the design of a large randomised trial.

10.2 PROPOSED ANALYSES

Measures to be reported:

Primary outcome data

1. Trial uptake: eligible participants as compared with recruitment.

Secondary Outcome Data

- 1. Routine participant demographics including past medical history and drug history
- Any additional treatments received during inpatient stay (including magnesium sulphate, antibiotics, syntocinon / other methods of induction/augmentation and steroids)
- 3. Retention, adherence and ability to collect clinical outcomes from participants
- 4. Time from presentation with threatened preterm labour to delivery of first dose of IMP.
- 5. Time from presentation to acute care and assessment services with suspected preterm delivery to delivery itself, as well as gestation at delivery
- 6. Contraction frequency during treatment course, from presentation to delivery or cessation of regular uterine activity.
- 7. Bloods: Liver function tests, creatinine kinase levels (side effects), maternal and cord inflammatory profile (see 2.2.2 for details of measures within the inflammatory profile).
- 8. Compliance with treatment
- 9. Adverse events
- 10. Acceptability of the trial following completion of the protocol
- 11. Other clinical outcomes
 - a. Maternal outcomes:
 - i. Proven maternal infection (See Appendix 4: Glossary of Terms for definition)

CR007-T01 v4.0 PIPIN Protocol Version 5.0 17/05/2019 Page **29** of **45**

- ii. Safety of intervention to mother (self-reported AEs and biochemical monitoring of liver function tests and creatinine kinase).
- iii. Pre-labour ROM
- iv. Duration, location and level of care of hospital stay following presentation with suspected preterm labour AND following delivery.
- b. Neonatal morbidity and mortality, safety of intervention, gestational age at delivery, birthweight, duration, location and level of care required following delivery. If in utero transfer occur, cause of method of transport used.
- 12. Pharmacokinetics of pravastatin

Participant uptake the study will involve a direct analysis of eligible participants presenting to acute care and assessment services compared with recruitment. Secondary outcomes 1 and 2 will be used to perform subgroup analysis and identify potential confounders between treatment and placebo arms. Outcomes 3 - 11 will be used to directly compare treatment and placebo arms of the trial, and inform design for a large scale trial in the future.

A formal statistical analysis plan will be completed and signed off before study unblinding.

Analysis will be performed on an intention to treat basis to minimise possible bias. Whilst every effort will be made to ensure completeness of data sets, sensitivity analyses will be performed to evaluate data robustness. Further detail can be reviewed in the Statistical Analysis Plan.

No interim analysis is planned at this time.

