2.1.2 Secondary Objectives

Overall, the goal of this study is to inform design of a multicentre randomised controlled trial, and the secondary objectives are based on aspects of this.

- 1) To evaluate whether administration of pravastatin when compared with placebo to women in preterm labour is associated with prolonged time to delivery, a reduction in contractions, and lower maternal and fetal markers of inflammation without adverse effects.
- 2) To evaluate whether administration of pravastatin when compared with placebo to women in preterm labour improves maternal and fetal outcomes
- 3) To monitor the average time from a participant's first contact with medical staff to delivery of the first dose study drug.
- 4) To ascertain the acceptability of the study design to participants after completion of the protocol.
- 5) Record participant compliance with treatment
- 6) To describe the pharmacokinetics of pravastatin in the study population as compared with published parameters.

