4.3 EXCLUSION CRITERIA

- Immediate delivery deemed necessary for fetal or maternal reasons as determined by a senior clinician.
- Pre-labour, preterm rupture of membranes in the index pregnancy
- Obstetric Cholestasis as defined by RCOG (RCOG Green-Top Guideline, Number 43)
- Established severe pre-eclampsia or HELLP syndrome as defined by NICE guidance (Hypertension in pregnancy: diagnosis and management | Guidance and guidelines | NICE n.d.)
- Known History of hepatic or renal impairment
- Ingestion of drugs thought to alter the pharmacokinetics or efficacy of statins, including erythromycin and/or nifedipine.
- Taking any one of the prohibited drugs as listed the SmPC and in 6.7.3
- Lactose intolerance (due to excipient in Pravastatin and placebo)
- Current or previous alcohol misuse
- Personal or first degree relative with heritable muscle disorders
- Participating in another CTIMP trial

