5.5 RANDOMISATION

5.5.1 Randomisation Procedures

Participants will be randomised to active or placebo in a 1:1 ratio. Randomisation block size will use permuted blocks of size 2, 4, and 6, randomly sorted, and spliced with occasional randomly inserted simple runs of random length to aid unpredictability. Randomisation codes will be provided to ISG by ECTU, and packs dispensed in a sequential fashion from these. Details of the study pack number allocated will be recorded in the Participant's notes, on the medication record as well as in the drug accountability log in the treatment room of labour ward.

This trial will be double blinded. Randomisation codes will be held by both ECTU and the local Pharmacy department.

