6.3 DOSING REGIME

Participants will receive 1 dose orally per 24 hour period +/- 6 hours for a total of 7 days. The drug will be dispensed immediately following randomisation from the stock in labour ward and administered at 24 hour intervals or as close to this as is practicable thereafter. The maximum dose will be one tablet in 24 hours with provision for two tablets within a 24 hour period should this enable a more practical regime (i.e. if first dose is taken at 0100, we will allow second dose at either 2200 the same day, or 0700 the following). Participants will self-dispense following the first dose, and record the time taken in their individual diaries. They will be encouraged but not enforced to take the dose at the same time each day.

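### Section 10.2 uses treatments given at any time in the inpatient stay, including those begun after randomisation, as subgroup factors and candidate confounders; this can bias the pravastatin–placebo comparison

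*Protocol*

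**What the plan says.** Section 10.2 of the protocol lists the secondary outcome data. The first entry is demographics with medical and drug history. The second is "Any additional treatments received during inpatient stay (including magnesium sulphate, antibiotics, syntocinon / other methods of induction/augmentation and steroids"). The section then assigns a role to both entries: "Secondary outcomes 1 and 2 will be used to perform subgroup analysis and identify potential confounders between treatment and placebo arms". The next sentence gives the main comparison: "Outcomes 3 - 11 will be used to directly compare treatment and placebo arms of the trial". The same section adds: "Analysis will be performed on an intention to treat basis to minimise possible bias". It leaves further detail to a statistical analysis plan to be signed off before unblinding.

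Nothing in 10.2 limits the second entry to treatments given before randomisation. Other sections bear on the timing:

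- Section 6.3: "The drug will be dispensed immediately following randomisation from the stock in labour ward".
- Section 4.3 excludes women with "Immediate delivery deemed necessary for fetal or maternal reasons as determined by a senior clinician".
- Section 2.1.2 gives the effects looked for in the pravastatin arm: "prolonged time to delivery, a reduction in contractions, and lower maternal and fetal markers of inflammation".

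**The concern.** A confounder is a common cause of treatment and outcome. In a trial where "Participants will be randomised to active or placebo in a 1:1 ratio", allocation has no such cause. A treatment started after allocation may be a consequence of it. If pravastatin slows labour or lowers inflammation, it may change who receives syntocinon, augmentation, antibiotics, steroids or magnesium sulphate. Women who receive such a treatment in one arm are then no longer comparable with those who receive it in the other, and splitting or adjusting by it gives up the protection of randomisation.

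The comparison at risk matters. Section 10.1 says that time to delivery and contraction frequency, with recruitment rate and acceptability, will help decide whether a large trial is warranted. A distorted subgroup or adjusted result on either outcome could colour that decision.

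**Working it through.** **Timing.** Study drug follows randomisation at once (6.3), and women needing immediate delivery are not enrolled (4.3). Syntocinon and other induction or augmentation therefore fall almost wholly after allocation. Steroids, magnesium sulphate and antibiotics may fall on either side of it: section 5.2 lets a woman take the time she needs to decide, and 2.2.2 treats the interval from first being seen to first dose as an endpoint in its own right.

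**Size.** The protocol gives no figure to reproduce: section 10.1 has no power calculation, and no rate of use of these treatments is stated. All inputs below are assumptions.

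*Scenario.* Delivery within 7 days: 60% on placebo, 40% on pravastatin, a true difference of -0.20. Syntocinon goes to 50% of those who deliver and 10% of those who do not.

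| Arm | Syntocinon: delivered / all | No syntocinon: delivered / all |
|---|---|---|
| Placebo | 0.30 / (0.30 + 0.04) = 0.30 / 0.34 = 0.882 | 0.30 / (0.30 + 0.36) = 0.30 / 0.66 = 0.455 |
| Pravastatin | 0.20 / (0.20 + 0.06) = 0.20 / 0.26 = 0.769 | 0.20 / (0.20 + 0.54) = 0.20 / 0.74 = 0.270 |

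Stratum differences: 0.769 - 0.882 = -0.113 with syntocinon; 0.270 - 0.455 = -0.184 without (from unrounded values).

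Mantel-Haenszel weights, w = n1·n0/(n1 + n0): 0.26 × 0.34 / 0.60 = 0.1473 and 0.74 × 0.66 / 1.40 = 0.3489.

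Pooled difference: (0.1473 × -0.1131 + 0.3489 × -0.1843) / (0.1473 + 0.3489) = -0.0810 / 0.4962 = -0.163.

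So -20 points becomes about -16, a loss of about 18% of the effect.

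*No-bias case.* If 34% receive syntocinon in each arm regardless of delivery, the syntocinon stratum gives 0.204/0.34 = 0.60 on placebo and 0.136/0.34 = 0.40 on pravastatin. The difference is -0.20, with nothing lost.

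*Range.* A simulation (2 million women per row, 1:1) used log time to delivery as outcome. An unmeasured labour severity (SD 1) raises the log-odds of the later treatment by 1 per SD and shortens log time by 0.7 per SD; residual SD is 0.7.

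| Use, placebo / pravastatin | Later treatment's own effect | Randomised difference | Adjusted for later treatment |
|---|---|---|---|
| 50% / 50% | none | 0.00 | 0.00 |
| 50% / 30% | none | 0.00 | -0.11 |
| 50% / 30% | none | 0.50 | 0.39 |
| 50% / 40% | -0.5 | 0.55 | 0.44 |
| 50% / 30% | -0.5 | 0.60 | 0.39 |

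The shift runs from zero, when allocation leaves use unchanged, to about -0.2. In the last two rows part of the gap is a genuine drug effect that acts through the later treatment and is removed by adjusting for it.

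**The case against.** The strongest reply is that the randomised comparison survives. Section 10.2 keeps a direct comparison of arms for outcomes 3 to 11, states no adjusted model, and speaks only of identifying possible confounders. The primary outcome is uptake, which no later treatment can touch. This is a 40-woman feasibility study with no formal efficacy claim, and a statistical analysis plan is still to come. All of that stands and limits the severity. It does not remove the point: the subgroup use is explicit, and a statistical analysis plan that followed 10.2 would carry it forward.

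Four stronger readings are tempting and are not supported.

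- A reader might infer that every treatment in the second entry is given after randomisation. The text gives no timing, and some steroids, magnesium sulphate or antibiotics may come first; those are legitimate baseline factors.
- A reader might infer a contradiction with intention to treat. Women can be analysed as allocated within an ill-chosen subgroup, so there is none.
- A reader might infer that covariates will be picked on chance imbalance. Section 10.2 gives no selection rule.
- A reader might infer that the effect in this trial would be reversed or manufactured. The worked scenario shows attenuation only. The spurious -0.11 in the simulation depends on an assumed drop in use from 50% to 30% together with an assumed unmeasured severity factor; the documents supply neither.

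**Conclusion.** The point holds in a limited form. Section 10.2 assigns treatments from the whole inpatient stay to subgroup analysis and the search for confounders. For those begun after randomisation, most clearly syntocinon and other induction or augmentation, that role is wrong, and conditioning on them can bias the comparison of arms. Whether it does depends on whether allocation changes their use, which the protocol cannot tell us. The size is illustrative only: nil if use is unaffected, and -20 points becoming -16 in the one tabulated scenario. The uptake endpoint and the direct comparison of outcomes 3 to 11 are unaffected. It should be fixed because two of the outcomes exposed to it inform the large-trial decision, but it does not threaten the trial's primary purpose.

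**What to change.** Reword the sentence in section 10.2 so that subgroup factors and any adjustment variables are confined to data fixed before randomisation: the first entry (demographics, medical and drug history), gestational age at screening (already in the section 7.2 schedule), and treatments documented as started before randomisation. State that treatments started after randomisation will be reported only descriptively, by arm. Carry the same wording into the statistical analysis plan.

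The cost is a sentence or two and no new assessment. The start time of each treatment relative to randomisation must be available; section 8.1 already names medication charts as source data, so it should be recoverable from them.

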2.2.2 Secondary Endpoints

Secondary Endpoints:

- 1) Retention, adherence and ability to collect clinical outcomes from participants
- 2) Time to delivery from presentation and gestation at delivery
- 3) Contraction frequency as monitored at presentation and from randomisation to delivery or cessation of regular uterine activity.
- 4) Maternal markers of inflammation including, but not limited to: IL-6, IL-10, IL-13, IL-17, TNFa, IL-1RA, sTNF-RI, sTNF-R2, and HO-1, as well as levels of the soluble IL-6R and the inhibitor spg130 (abbreviated hereafter to 'Inflammatory Profile')
- 5) Fetal measures of inflammation including but not limited to: (cord IL-1, IL-6, IL-8, sIL-6R and sgp130.
- 6) Adverse events (maternal and fetal)
- 7) Time from time first seen in an acute obstetric care setting to administration of trial medication as documented in the participant medical records.
- 8) Compliance with 7 days of blinded treatment
- 9) Acceptability of the trial to those who have participated
- 10) Pharmacokinetic parameters as compared with current published data
- 11) Maternal outcomes:
 - a. Proven maternal infection
 - b. Safety of intervention to mother (self-reported AEs and biochemical monitoring of liver function tests and creatinine kinase).
 - c. Pre-labour ROM
 - d. Duration, location and level of care of hospital stay following presentation with suspected preterm labour AND following delivery.
- 12) Neonatal outcomes:
 - a. Details of in utero transfers including mode of transport required
 - b. Gestational age at delivery, morbidity and mortality, birthweight, duration and location of hospital stay post-delivery and up to 28 days post EDD.
 - c. Safety of intervention

CR007-T01 v4.0 PIPIN Protocol Version 5.0 17/05/2019 Page **14** of **45**

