4. STUDY POPULATION

4.1 NUMBER OF PARTICIPANTS

We will to recruit 40 participants. Eligible participants are pregnant women presenting in preterm labour at 24+0 to 35+6 weeks gestation. Preterm labour is defined as regular uterine activity with either a positive fetal fibronectin (See Appendix 5) or evidence of cervical change as monitored through cervical length scanning or direct observation of dilation.

We estimate a duration of 2 years with an 18 month recruitment period. Follow up of participants to last Participant last visit will take up to another 6 months.

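### The contraction-frequency outcome has inconsistent windows, and the analysis section starts it at presentation, before randomisation and first dose

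*Protocol*

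**What the plan says.** The contraction outcome is defined in three places.

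- Section 10.2, item 6: "Contraction frequency during treatment course, from presentation to delivery or cessation of regular uterine activity".
- Trial Summary, secondary endpoint 3: also runs from presentation, without mentioning randomisation.
- Section 2.2.2, item 3: "Contraction frequency as monitored at presentation and from randomisation to delivery or cessation of regular uterine activity".

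Section 10.2 then states that "Outcomes 3 - 11 will be used to directly compare treatment and placebo arms of the trial". It names demographics, history and additional inpatient treatments as the source of subgroups and possible confounders, and names no model for any outcome. Section 10.1 says of recruitment rate, time to delivery, contraction frequency and acceptability that "this will be used to determine whether a large randomised trial is warranted and feasible".

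A pre-treatment reading exists for both kinds of biological outcome. Section 4.2 requires at least one palpable contraction in 20 minutes of CTG for entry. For the blood markers, Section 7.2 C says "an inflammatory profile will be obtained twice on day 1 (baseline and at or around 12 hours post dose"; Section 7.2 B places the first sample after consent and randomisation.

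Section 3 limits hourly contraction recording to women contracting at least once in 10 minutes after randomisation. It continues until delivery or until four consecutive hours below that rate. Section 3 also describes daily recording of contractions over the treatment period.

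**The concern.** Presentation comes before consent, randomisation and first dose. A reading taken then cannot have been changed by pravastatin, so it belongs on the baseline side of a comparison of arms. Item 6 describes its window as the treatment course and, in the same line, starts it before treatment. An analyst following item 6 and one following Section 2.2.2 could build different outcomes from the same records.

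Two related points concern the use of baseline values. The baseline inflammatory sample is taken after randomisation, while Section 6.3 has the drug dispensed immediately after randomisation, and nothing expressly requires the blood to come first. The hourly recording rule also selects women on something observed after randomisation, so a comparison resting only on hourly records would not be a comparison of the randomised groups.

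At stake is the reading of one of the few outcomes that Section 10.1 feeds into the decision on a large trial.

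**Working it through.** **Stated inputs.** The protocol says "We will to recruit 40 participants" and "Participants will be randomised to active or placebo in a 1:1 ratio", so about 20 per arm. On power it says "A formal power calculation is not considered necessary or appropriate for a feasibility study"; there is therefore no figure to reproduce. Effect size, SD, correlation, number of readings and summary measure are not given, and all values for them below are assumptions.

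**Step 1: dilution if readings are averaged.** Let the treatment shift each of k post-randomisation readings by d and leave one presentation reading unchanged. The mean of all k + 1 readings then differs between arms by d × k/(k+1), and the share lost is 1/(k+1).

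| k | share kept | share lost |
|---|---|---|
| 1 | 0.50 | 50% |
| 4 | 0.80 | 20% |
| 6 | 0.86 | 14% |
| 12 | 0.92 | 8% |
| 24 | 0.96 | 4% |

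Two of these can be tied to the recording rules. Under Section 3, a woman in hourly recording whose contractions settle at once contributes four hourly readings, so k = 4. A woman with one diary reading a day for at most 7 days has k of at most 7, a loss of at least 1/8 = 12.5%.

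**Step 2: what this could do to the comparison.** Assume d = 0.8 SD, k = 4, correlation 0.5 between any two readings, 20 per arm, two-sided 5%, and power = Φ(standardised effect × √(20/2) − 1.96).

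- Post-randomisation mean only: variance (1 + 3 × 0.5)/4 = 0.625; effect 0.8/√0.625 = 1.012; power 89%.
- Presentation reading averaged in: difference 0.8 × 0.8 = 0.64; variance (1 + 4 × 0.5)/5 = 0.60; effect 0.64/√0.60 = 0.826; power 74%.
- Presentation reading as covariate: variance 0.625 − 0.25 = 0.375; effect 0.8/√0.375 = 1.306; power 98.5%.

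The same reading costs information inside the outcome and adds it as a covariate. The normal approximation is slightly generous: for 0.8 SD on a single unadjusted reading it gives 72%, against 69% from the t-test.

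**Step 3: gain from baseline adjustment of a single follow-up reading.** Residual variance is (1 − ρ²) × SD². The difference detectable with 80% power is 2.80 × √(2/20) = 0.886 SD unadjusted, and this times √(1 − ρ²) adjusted.

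| ρ (assumed) | variance falls by | detectable difference | equivalent unadjusted N |
|---|---|---|---|
| 0.3 | 9% | 0.845 SD | 40/0.91 = 44 |
| 0.5 | 25% | 0.767 SD | 40/0.75 = 53 |
| 0.7 | 49% | 0.633 SD | 40/0.51 = 78 |

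**Step 4: who is recorded.** Entry needs one contraction in 20 minutes (Section 4.2); hourly recording needs one in 10 minutes after randomisation (Section 3). Women between the two thresholds are randomised but fall outside the hourly series. Their later data come from the diary or inpatient CTG (Section 7.2 D).

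**The case against.** A reader might infer that the arms will be compared without their baseline values. The protocol does not support that. A direct comparison of arms is not the same as an unadjusted one, and an analysis of covariance compares arms directly too. Naming demographics and inpatient treatments as sources of confounders does not exclude other covariates. The closing part of Section 10.2 defers further detail to a statistical analysis plan to be signed off before unblinding. Choice of model and covariates is ordinary content for that plan, so a missing adjustment is not established, and Step 3 shows only what adjustment could bring.

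A reader might also take the dilution as certain. It is not: it arises only if the presentation reading is averaged with later ones, and no summary measure is stated. Section 2.2.2 can be read as a baseline followed by a series, and with many hourly readings the loss is small.

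Nor does the decision argument reach the inflammatory markers. Section 10.1 places them among the remaining outcomes, used for safety or to inform design. That the baseline sample precedes the first dose is already implied, since Section 7.2 contrasts it with the 12-hour post-dose sample and Appendix 2 labels it as baseline.

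All of this stands. It does not remove the conflict between the windows. Item 6 and the Trial Summary start the outcome before treatment, and an analysis plan must either follow that wording or depart from it.

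**Conclusion.** The point holds for the contraction window. Two of the three definitions start at presentation, the third separates presentation from randomisation, and item 6 as written puts a reading that treatment cannot affect inside an outcome used for the decision on a large trial. If readings are averaged, 1/(k+1) of any true difference is lost: from 50% at k = 1 to 4% at k = 24, with k assumed.

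An explicit commitment to baseline adjustment is a worthwhile addition, not the correction of a proven omission. Its gain, a variance reduction of 9% to 49%, rests on assumed correlations of 0.3 to 0.7. It does not extend to cord markers, which have no baseline. These are secondary outcomes of an unpowered feasibility study, and the primary endpoint is unaffected.

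**What to change.** 1. In the Trial Summary, Section 2.2.2 item 3 and Section 10.2 item 6, start the contraction outcome at randomisation. Label the presentation CTG value as baseline, to be used only as a covariate.
2. In Section 7.2 B, state that the baseline inflammatory sample is drawn before the first dose.
3. In Section 10.2, add that maternal inflammatory markers and contraction frequency are compared between arms with adjustment for their own baseline value, with model details left to the SAP.
4. In the same place, state that the contraction comparison covers all randomised women, using diary or CTG data for those outside the hourly recording rule.

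The cost is wording in four places, submitted as a protocol amendment, and one degree of freedom per model. No new measurements or participants are needed. The wording should be settled before unblinding.
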